
Primary Objectives

We will study the effectiveness of highly innovative transplant social worker led interventions that intervene on key knowledge, interpersonal, logistical and financial barriers to live kidney donation for African Americans patients on the deceased donor kidney waiting list.

Objectives and Hypothesis

- A. Transplant Social Worker Educational and Behavioral Intervention.** In our previous work, we developed the Talking About Live Kidney Donation Social Worker Intervention (TALK SWI), a culturally sensitive educational and behavioral intervention to improve consideration and pursuit of live donor kidney transplants among patients with chronic kidney disease (CKD) and their families. TALK SWI is tailored to accommodate patients with low reading (i.e., 4th grade) and health literacy levels and helps patients and their

families overcome self-identified interpersonal barriers to discussing and pursuing live donor kidney transplants. TALK SWI educational materials were determined to be culturally sensitive based on our conduct of 8 focus groups of African American and non-African American patients with chronic kidney disease (with and without live donor kidney transplant experience) and their family members identifying their concerns about live donor kidney transplantation¹⁹. In a recently completed randomized controlled trial, we found TALK SWI was effective in improving rates of consideration and pursuit of pre-emptive live donor kidney transplantation among patients with stage 4 CKD not yet on dialysis.²² We propose to study the effectiveness of the TALK SWI intervention to activate live kidney donation among African Americans who have recently registered on the transplant waiting list. We hypothesize the TALK SWI will be a powerful catalyst to increase live kidney donation for these patients who have already overcome some barriers to live donor kidney transplantation (i.e., completed the transplant evaluation).

B. **Transplant Social Worker Financial Assistance Intervention.** We hypothesize a financial assistance intervention delivered by transplant social workers to help patients and their potential donors overcome logistical and financial obstacles to live donor kidney transplantation will be well-received by social workers, patients, and their families.

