If effective, our financial intervention will provide a rationale for potentially expanding current National Live Donor Assistance Center (NLDAC) policies. In a separately funded study, we are currently testing the effectiveness of a financial assistance intervention to improve access to live donor kidney transplantation among patients with end stage renal disease (ESRD) who are not yet on the transplant waiting list. We hypothesize that patients who are on the waiting list and highly motivated to receive a kidney (who we propose to study in this application) will view this intervention favorably. **The current study leverages our substantial previous work to develop and test these interventions. Our proposed study is a distinct and novel extension of our previous work in three ways:** (1) Placing the TALK SWI and the Financial Assistance Intervention in the transplant social work environment: Neither intervention has previously been studied in the transplant center, although this is a place where social workers are already routinely employed in clinical care. Social workers have all the skills necessary to execute both interventions, making this proposal a natural extension of our prior work. (2) Studying patients on the deceased donor transplant waiting list: We have not previously employed either intervention among patients waiting for a deceased donor kidney. Because these patients are highly motivated to receive kidneys, employing the interventions among this population could prove highly effective. (3) Combining TALK SWI with the Financial Assistance Intervention: We have not previously employed these interventions simultaneously. Because the interventions address distinct key barriers to African Americans' receipt of live donor kidney transplantation, we hypothesize combining them could have an additive effect in overcoming barriers to live donor kidney transplantation. To enhance the perceived long-term relevance of our interventions to African Americans, we will measure the cultural competence of the transplant social worker interventions using established measures developed by the Agency for Health Care Research and Quality³⁵ and tailor the interventions to enhance their cultural competence based on our findings.

Background and Significance

Promise of Live Donor Kidney Transplantation to Address Disparities in Access to

Kidney Transplants for African Americans

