Arm 1. Usual Care (N=100): Participants randomly assigned to this arm will receive their usual care with the transplant team while awaiting a deceased donor kidney transplant. Participants are periodically contacted (approximately once per year) to establish their continued desire to be listed on the waiting list and to address any administrative issues related to transplant (i.e., updated contact and insurance information) by the DKPTP. They will be mailed the booklet and video at the end of the study.

Arm 2. TALK SWI (N=100): Participants randomly assigned to this arm will receive the TALK SWI delivered by a transplant social worker.

Arm 3. TALK SWI Plus Financial Assistance (N=100): Participants randomly assigned to receive the TALK SWI Plus the Financial Assistance for Living Donor Expenses will receive the TALK SWI as described for Arm 2. Study staff will also provide participants with information about the study Live Donor Financial Assistance Intervention, and provide instructions on how to use the Intervention (details on Financial Assistance Intervention described above)

D. Study Outcomes and Assessments: We perform assessments at baseline, 4 months and 12 months for all participants in Arms 1, 2 and 3. Transplant coordinators at DKPTP routinely capture names and contact information of potential donors contacting the center to inquire about donation procedures on potential recipients' behalves and enter it in the Phoenix (PHX) transplant application, which is part of the EpicCare Ambulatory

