Potential Live Kidney Donor Participants: Potential live kidney donors will only become aware of the Donor Financial Support Intervention through referrals by patient participants randomized to ARM 3 who voluntarily choose to make potential donors aware on their own accord, without prompting from study staff or the study Social Worker. Study staff and the study Social Worker will not contact or attempt to contact any family, friends, or acquaintances of enrolled patient participants. Patient participants in ARM 3 will be given a brochure (by study staff after the first TALK SWI meeting) for the donor financial support program and encouraged to share the information with people.

We will advise patient participants to ask potential donors to contact us directly only for questions related to the financial program. The financial assistance program being offered as part of this study is intended to provide reimbursement only in those circumstances when payment cannot reasonably be covered by other sources of reimbursement. Under Federal law, reimbursement to any living organ donor for travel and other qualifying expenses may only be provided if the donor cannot receive reimbursement for these expenses from any of the following sources:

1. any State compensation program, an insurance policy, or any Federal or State health benefits program;
2. an entity that provides health services on a prepaid basis; or
3. the recipient of the organ.

All persons who wish to become living organ donors are eligible to receive reimbursement from this study for their travel and qualified expenses if they cannot receive reimbursement from the sources outlined above and if they meet all the requirements for donor reimbursement as outlined below:

1. prove that they are either U.S. citizens or lawfully admitted residents of the U.S.;
2. have primary residence in the U.S. or its territories;
3. travel is originating from the donor's primary residence;
4. donor and recipient attest to full compliance with section 301 of the National Organ Transplant Act (NOTA), as amended (42 U.S.C. 274e) which stipulated in part "**** (i) it shall be unlawful for any person to knowingly acquire, receive, or otherwise transfer any human organ for valuable consideration for use in human transplantation if the transfer affects interstate commerce. The preceding sentence does not apply with respect to human organ paired donation*";

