members and friends they want to take part in the second session. Study staff will attempt to schedule the call at that time. They will ask the patient participant if they want to provide a number to receive a text and/or an email address, or prefer a mailed letter with the appointment date, time and toll-free WebEx phone number and access code to call in to a social worker session with the study Social Worker. They will be asked to share the call-in information with family/friends who may want to join the second SWI session.

n) **In-person SWI:** Study staff will administer a brief 10-minute hardcopy questionnaire to the patient participant immediately following the Social Worker session to obtain feedback about the acceptability of the TALK SWI. We will provide assistance with reading the questions and checking the responses if needed. **Telephone SWI:** Once the SWI session is complete, the Social Worker will ask the patient participant to remain on the line to schedule their next session, complete their post assessment and paperwork for payment. The Social Worker will leave the call and immediately notify one of the other study staff to join the call and
1) administer the brief 10-minute questionnaire 2) complete the paperwork required for payment; and, 3) if in Arm 3, see item (o) below.

Financial Intervention (Arm 3 only)

o) **In-person SWI:** Patient participants in ARM 3 will briefly meet with study staff immediately following their first session with the study Social Worker. Study staff will provide and review a brochure and materials for the donor financial support with patient participants. Patient participants will be encouraged to share the information with family members, friends and acquaintances if they desire, and to have potential donors contact study staff if interested.
Telephone SWI: Patient participants in ARM 3 will briefly review and discuss the brochure and materials they received in the mail for the donor financial support with study staff during the first SWI call. Patient participants will be encouraged to share the information with family members, friends and acquaintances if they desire, and to have potential donors contact study staff if interested. Study staff will mail additional copies of the materials if needed.

TALK Social Worker Intervention (Arms 2 and 3 only)

p) Study staff will mail patient participants a thank you note and \$50 check for completing the first session with the study Social Worker.

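### Objective B hypothesises that a donor fund delivered by social workers will be well received, but study staff run every described fund step and no described measure records an opinion of the fund

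*Protocol*

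**What the plan says.** In the Protocol, Objectives and Hypothesis, item B proposes "a financial assistance intervention delivered by transplant social workers" and predicts that it "will be well-received by social workers, patients, and their families". The same item repeats the prediction for waiting-list patients, who "will view this intervention favorably". The Abstract likewise counts the financial component among two interventions led by social workers.

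The operational text assigns the work differently. Under Study Design, Arm 3, "Study staff will also provide participants with information about the study Live Donor Financial Assistance Intervention" and explain how to use it. On opinion, Subject Recruitment and Compensation, Patient Participants, items n and t, has patients complete a short questionnaire "immediately following the Social Worker session to obtain feedback about the acceptability of the TALK SWI".

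The Protocol's paragraph on Intervention Fidelity and Uptake plans three fund measures: whether Arm 3 patients told others about the fund, family members' inquiries about using it, and the types and amounts of expenses reimbursed. SAP section 1.1.2 plans a summary of use of the fund. The only satisfaction it plans to summarise is satisfaction with the sessions. SAP section 1.2.2 states that these aims are descriptive and carry no formal test.

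**The concern.** A hypothesis needs an intervention delivered in the way it describes and a measure of what it predicts. Objective B appears to lack both. Being well received is an opinion, held here by three named groups, about a fund delivered by a named profession. If staff deliver the fund and no opinion of it is collected, the trial could end with its stated hypothesis for one of its two interventions unanswerable. A report could then claim that transplant social workers can acceptably deliver a donor reimbursement fund, a claim the trial would not have examined. That would matter because the Protocol presents the fund as a possible rationale for widening national donor-assistance policy.

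**Working it through.** The plan gives no figure to reproduce here. The check sets the hypothesis against the described procedures and measures.

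**Step 1: who performs each fund step.**

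| Fund step | Protocol location | Performed by |
|---|---|---|
| Mail pamphlet and forms after baseline | Patient Participants, item e | Study staff |
| Give information and instructions | Study Design, Arm 3 | Study staff |
| Hand over or review brochure | Selection of Subjects (potential donors); Patient Participants, item o; Potential Live Donor Participants, item a | Study staff |
| Take donors' calls, mail materials, consent and enrol | Potential Live Donor Participants, items b to d | Study staff |
| Send reimbursement checks | Potential Live Donor Participants, item e | Study staff |

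The Social Worker could be counted among the study staff, but item n separates the roles. In the telephone format the Social Worker leaves the call and another staff member joins for the questionnaire, the payment paperwork and the Arm 3 fund step. No described fund step is given to the Social Worker.

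**Step 2: what each described opinion measure is about.**

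| Measure | Location | Object |
|---|---|---|
| Patient questionnaire after each session | Protocol, Patient Participants, items n and t | TALK SWI |
| Family/friend questionnaire | Protocol, Family/Friend Participants, sections 1 and 3 | TALK SWI and the session |
| Cultural competence items | Protocol, Assessment of Environment and Intervention Cultural Competency | The transplant program, its social workers and TALK SWI |
| Satisfaction | SAP 1.1.2, aim 2 | Sessions |

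SAP section 3.2 adds awareness and receipt of assistance programs (item 4), concerns about live donor transplant (item 5) and personal financial well-being (item 6). None asks for a view of the fund.

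**Step 3: coverage of the hypothesis by named group.**

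| Group | Described opinion of the fund | Indirect evidence |
|---|---|---|
| Patients | None | Telling others; use |
| Families (and potential donors) | None | Inquiries; reimbursed expenses |
| Social workers | None | None |

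Groups with a described opinion measure: 0 of 3. Groups with indirect evidence: 2 of 3. Social workers' input in Study Phase 1 concerned adapting the TALK SWI protocol, so it does not fill the third row.

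**Step 4: whether an answerable hypothesis already exists.** It does. Objective B suggests that the two interventions combined could have an additive effect, and the Conceptual Framework predicts that the paired arm will be the most effective. Both concern what the fund adds to TALK SWI, which is an Arm 3 versus Arm 2 question. In the SAP 4.1.2 models, with Arm 1 as reference:

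- Arm 2 versus Arm 1: β1
- Arm 3 versus Arm 1: β2
- Arm 3 versus Arm 2: β2 − β1, with variance Var(β1) + Var(β2) − 2Cov(β1, β2)

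The SAP states interest in β1 and β2 only. The Kruskal-Wallis comparison in SAP 4.1 is a joint test across three arms and does not isolate the fund. The needed contrast comes from the planned model without refitting, but it is not stated.

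**The case against.** The strongest reply is that the plan does collect fund-specific behaviour, and that behaviour is a reasonable sign of reception. This partly stands. Disclosure, inquiries and spending are indirect evidence for patients and families, and a patient can tell relatives about the fund without having a donor. A reader might infer that the trial yields no data at all bearing on reception, and the documents do not support that. Behaviour is still not a view. Low use may mean that no donor came forward or that another source paid, no level of use is defined as well received, and nothing reaches social workers.

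Other stronger readings are tempting and should not be adopted:

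- **No instrument asks about the fund.** The questionnaires and the SAP appendix are not in the available text, and the follow-up calls last about 60 minutes. An unlisted item is possible. The supportable statement is that none is described.
- **The Protocol bars the Social Worker from delivering the fund.** The phrase "without prompting from study staff or the study Social Worker" restricts both roles equally and concerns patients choosing to tell donors. It does not settle who delivers the fund.
- **Social workers have no financial role.** TALK SWI makes them a contact point on financial assistance, and Phase 1 built the materials they usually provide into the protocol. That role belongs to TALK SWI, which Arms 2 and 3 share, so it is not delivery of the fund.
- **Thirty of 100 Arm 3 patients would count as poor reception.** The Protocol forecasts that 70% of 100 will have a donor who uses the fund, which leaves 100 − 70 = 30. No passage treats non-use as poor reception.
- **The telephone questionnaire comes too early.** At session 1 it is listed before the fund discussion. However, the pamphlet is mailed after baseline and a second questionnaire follows session 2, so the order matters little.

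It can also be said that reception is not a listed outcome in the SAP, so no planned estimate or test changes. That is correct and limits the weight of the point.

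**Conclusion.** The concern holds in a limited form. As worded, the Objective B hypothesis cannot be answered. Its delivery premise does not match the described procedures, 0 of 3 named groups has a described opinion measure for the fund, and social workers have no fund measure of any kind. The consequence falls on a stated objective and on what may be concluded from it. A reader might infer that the trial's main result is compromised, but the activation outcome, its ascertainment and its planned models do not depend on reception.

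The verdict assumes that the unseen questionnaires and SAP appendix contain no fund opinion item. If one exists and is cited, the measurement part falls for the groups it covers, while the mismatch over delivery remains. Which remedy is feasible depends on whether data collection is still open. The SAP suggests that it is complete: section 2.2 reports data acquisition in the past tense, section 4.1.1 refers to a final manuscript, and section 4.1.2.4 refers to only 4 transplant events.

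**What to change.** 1. **Wording.** In Objective B and in the conclusions, describe the fund as administered by study staff alongside a TALK SWI led by social workers. Draw no conclusion that social workers can acceptably deliver it.
2. **Hypothesis and contrast.** Rest Objective B on the effectiveness hypothesis already in Objective B and the Conceptual Framework. Add the Arm 3 versus Arm 2 contrast, β2 − β1 from the SAP 4.1.2 models, reported with a 95% CI. If outcomes are already known, disclose it as a late addition.
3. **Reception.** Keep the reception hypothesis only on one of two conditions. Either an existing questionnaire item on the fund can be cited, or collection is still open and items can be added: two or three in the Arm 3 session-2 questionnaire and the 4- and 12-month calls, plus a short item for the social workers. Otherwise report disclosure and use descriptively and state that reception was not measured.

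The cost is a narrower claim, one additional contrast from a model already planned and, only if items are added, a few minutes of participant time.

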Transplant Social Worker Support for Live Kidney Donation in African Americans

Statistical Analysis Plan
Document Date: August 3, 2020

NCT02369354

1 Study Overview

"The Talking about Living Kidney Donation Support (TALKS) study is a randomized controlled trial designed to test the incremental effectiveness of (1) a culturally sensitive educational and behavioral social worker intervention and (2) a live donor financial assistance intervention to improve potential kidney recipient activation (i.e., discussions with physicians and family about live donor kidney transplant [LDKT]) and live kidney donation among African American patients on the deceased donor kidney transplant waiting list at Duke University Medical Center."

1.1 Study Aims

1.1.1 Primary and Secondary Aim

To assess the effects of behavioral and financial interventions compared to usual care on 1) LDKT activation (primary) and 2) scenario movement (secondary). ("Table 2" in Appendix)

1.1.2 Tertiary Aims

1. Describe characteristics and correlates of pursuit of LDKT ("Table 3" in Appendix)
2. Summarize use of TALKS materials, attendance of TALK SWI sessions, and satisfaction with sessions. (Section 3 of Appendix)
3. Summarize use of financial assistance program
4. Summarize outcomes of donor inquiries (e.g., did it lead to evaluation, were they eligible, ineligible, etc.)

1.2 Study Hypotheses

1.2.1 Primary Hypothesis

Those in the two intervention groups will have higher levels of activation and scenario movement compared to those in usual care.

1.2.2 Secondary Hypotheses

These aims are descriptive and no formal hypotheses will be tested.

2 Study Population

2.1 Inclusion/Exclusion Criteria

The target population, and inclusion/exclusion criteria have been previously published (Protocol Paper, 2015). Briefly, participants were African-American adults (18+ years old) with ESRD on the transplant waiting list at Duke. They had no prior LDKT. Family members and friends were also recruited into the study to attend the SWI meetings.

The data consist of a baseline visit, a 4-month visit, and a follow-up visit. EHR data were also collected up to 12 months' post randomization.

2.2 Data Acquisition

Data were obtained via primary data collection through telephone surveys administered by study personnel. Study personnel entered the data into a REDCap database and the study statistician downloads the raw data directly from REDCap using the SAS export tool. EHR data are obtained from data

pulls from the Duke Kidney and Pancreas Transplant Program by [name]. The statistician converted these pulls to SAS datasets and the original pulls were archived. The data are stored on the GIM server under BoulwarePrivate/TALKS.

3 Outcomes, Exposures, and Variables of Interest

3.1 Primary and Secondary Outcomes

1. Live kidney donor activation (primary): per the protocol, “defined as the composite rate of live kidney donor inquiries on behalf of patient participants, completed live kidney donor transplant evaluations, and live kidney donor transplants in each arm, ascertained via medical records maintained by the Duke Kidney and Pancreas Transplant Program.”

In other words: For each participant, the total number of donor inquiries, evaluations, and LDKT over a 12-month period will be summed and defined as the live donor activation score. For example, if a participant had 5 inquiries, 2 evaluations, and an LDKT, then this person’s score would be 8.

In sensitivity analyses, we will look at these individually, and the composite at 24 months.

2. Pursuit of LDKT (secondary) (scenario): Assessed by two questions, Q1: “Has a family member or friend told you that they would give you a kidney?” And Q2: “Have you talked with family and/or friends about the possibility of someone giving you a kidney?”. Participants will be categorized into 3 groups: 3=identified a donor (answered “yes” to Q1); 2=talked with family members/friends but did not identify a donor (“no” to Q1 and “yes” to Q2); 1=did not talk to family members/friends (“no” to Q1 and Q2). Note that once a person has reached a level, he cannot regress to a previous level, e.g., if at level 2 at randomization, the person cannot be at level 1 at month 4.

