TALK SWI Adaptation Procedures. We reviewed the original TALK SWI protocol with transplant social workers and adapt the TALK SWI into their existing workflows. Adaptation focused on (1) ensuring the intervention provides adequately addresses patients’ communication and financial needs in social workers’ views, and (2) ensuring the intervention can be feasibly implemented and sustained by transplant centers long-term. For instance, we asked social workers to identify the resources they typically provide to patients and families concerned about the financial aspects of LDKT and we incorporated provision of these materials into the protocol. We also identified potential challenges transplant social workers typically encounter with TALK SWI implementation.

Study Phase 2 (Randomized Controlled Trial Phase)

We will perform a randomized controlled trial to assess the effectiveness of TALK SWI and the TALK SWI plus financial support intervention to improve rates of LDKT among African American potential transplant recipients on the deceased donor kidney waiting list at the Duke Kidney and Pancreas Transplant Program compared to usual care. We will follow potential recipients for 1 year via questionnaire and 2 years via medical records (post baseline questionnaire completion) to assess live kidney donor activation on their behalves (live donor inquiries, completed new live donor evaluations, or live kidney donation) (primary outcome). We will assess all primary outcomes at 1 year after baseline enrollment. We will also assess potential recipients’ self-reported behaviors reflecting their pursuit of LDKT, including their conduct of LDKT discussions with physicians and with their families and their identification of potential live donors.

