module. For our **primary outcome**, we will assess “live kidney donor activation”, defined as the composite rate of live kidney donor inquiries on behalf of participants (clinic records of individuals inquiring about the process of being considered for LDKT on participants’ behalves), completed live kidney donor transplant evaluations (recorded and tracked by transplant coordinators), and live kidney donor transplants (LDKT) in each arm after 12 months study enrollment. To determine which behaviors were most strongly activated by our interventions, we will also assess rates of these individual events in each arm in post-hoc analyses. **Secondary outcomes** will include measurement of behaviors reflecting patients’ and their families’ interest and pursuit of LDKT, including: self-reported LDKT discussions with physicians, self-reported LDKT discussions with family, and identification of a potential live donor. We will also assess several other **correlates** of participants’ willingness or ability to pursue LDKT, including their demographic characteristics, family function, self-efficacy with regard to decision-making about LDKT, perceptions of trust in their health care team. We will ask all participants about their use of any financial assistance programs, including the types and amounts of expenditures reimbursed. We also will track expenditures reimbursed specifically by participants in Arm 3. We will also passively follow participants for one additional year through their medical records to determine if participants achieve outcomes of interest after 1 year.

Assessment of Environment and Intervention Cultural Competency: We will measure the cultural competency of the DKPTP and transplant social workers using the Agency for Health Care Research and Quality CAHPS Cultural Competence Item Set³⁵, designed to capture patients’ perspectives on the cultural competence of health care providers. Items include information on (a) research subject-health care provider communication including shared decision-making; (b) experiences of discrimination due to race, ethnicity, insurance, or language; (c) experiences leading to trust or distrust; and linguistic competency. We will also add questions to ask specifically about the communication and shared decision-making skills of transplant social workers employing TALK SWI.

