4.2 Analysis Plan for Secondary Aim: Potential

Recipient Activation We will explore the crosstab of scenario by study arm cross-sectionally at each time and comparisons will be made via a chi-squared or Fisher’s exact test as appropriate.

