4.2.2 Dichotomous Formulation of Scenario

We will also dichotomize the scenario into maximum activation (talked with family/friends and identified a donor) vs less activation (talked with family/friends but did not identify a donor, or did not talk to family/friends). We will use a similar GEE (binomial outcome) to determine if the probability of having maximum activation over time is different between arms.

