4.2.3 Number of Steps Forward

The number of steps the participant moved forward at each follow-up visit will also be modeled with a GEE. Of interest is the number of steps moved from baseline to month 4, and from month 4 to month 12. All participants had baseline data. If participant was missing a M4 or M12 value, then 0 steps taken was imputed as the most conservative estimate. If participant was missing a value due to receipt of transplant, then the person was dropped from the analyses at the time of transplant reporting and thereafter.

Participants are not able to go back in scenario, thus if M4 scenario is less than baseline, or if M12 scenario is less than M4 (or baseline) then 0 steps will be imputed.

We will also fit a linear model looking at the total number of steps across the whole study, and a logistic regression model looking at any steps forward across the whole study as an outcome.

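### One of the protocol's three secondary outcomes, patient-reported LDKT discussion with physicians, has no definition, no arm comparison and no stated reason for omission in the SAP body.

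*SAP*

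**What the plan says.** In the protocol, section D (Study Outcomes and Assessments) lists the secondary outcomes as "self-reported LDKT discussions with physicians, self-reported LDKT discussions with family, and identification of a potential live donor". The Study Phase 2 overview repeats the list: "their conduct of LDKT discussions with physicians and with their families and their identification of potential live donors". The description of TALK SWI behavioral support gives the same three as the behaviours for which the social worker explores barriers. All three arms are due questionnaires at baseline, 4 months and 12 months.

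The SAP's Study Overview still counts physician discussions as part of recipient activation: "potential kidney recipient activation (i.e., discussions with physicians and family about live donor kidney transplant [LDKT". That is the SAP body's only mention of physicians. Section 1.1.1 then reduces the secondary aim to scenario movement. Section 3.1, item 2, defines the outcome: "Pursuit of LDKT (secondary) (scenario): Assessed by two questions". Q1 asks whether a relative or friend has offered a kidney, and Q2 asks whether the patient has raised the subject with family or friends. Section 4.2, headed as the analysis of potential recipient activation, opens with "We will explore the crosstab of scenario by study arm cross-sectionally at each time" and stays with scenario to the end.

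**The concern.** Physician discussion is tied to how the intervention is meant to work. The protocol abstract treats raising LDKT with physicians, as well as with relatives and friends, as the opening move towards a live donor, and the social worker sessions address it directly. It was also a declared secondary outcome.

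An analyst who follows the SAP body as written will produce no arm comparison for it. A reader who sets the results beside the protocol will find a named secondary outcome absent without explanation, and will be unable to tell whether it was not collected, judged unusable, or left out for some other reason. Nothing in the documents shows that anyone had seen results for this item. The SAP does, however, cite 4 LDKT events (section 4.1.2.4) and refer to the final manuscript (section 4.1.1), so some trial data were known when that text was written. That makes a stated reason more valuable.

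**Working it through.** No sample size, power or error-rate figure is involved, so the check sets the two documents side by side and counts.

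| Protocol secondary outcome | Where defined in SAP section 3 | Analyses in SAP 4.2 |
|---|---|---|
| Discussion with family | Scenario level 2 (Q2) | Through scenario |
| Potential donor identified | Scenario level 3 (Q1) | Through scenario |
| Discussion with physicians | None | None |

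**Outcomes carried over.** 3 named in the protocol − 2 present in scenario = 1 missing.

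**Tertiary outcomes (SAP 3.2).** The six are interest in LDKT, factual knowledge, perceived knowledge, knowledge of financial programs, concerns, and personal financial well-being. Physician-discussion items: 0 of 6.

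**Planned analyses (SAP 4.2 to 4.2.3).** Crosstab with chi-squared or Fisher's exact test (1) + continuous GEE (1) + binomial GEE (1) + GEE of steps forward (1) + linear model of total steps (1) + logistic model of any step (1) = 6. All use scenario; none uses physician discussion. The six are reworkings of one variable, so the count that matters is 2 of 3 outcomes carried over.

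**Can scenario register the missing behaviour?** Take a participant who answers no to Q1 and Q2 at baseline, which is level 1. By month 4 this person has begun discussing LDKT with a physician, but the answers to Q1 and Q2 are still no. Scenario stays at level 1, and the steps forward are 1 − 1 = 0. A participant already at level 3 at baseline cannot move at all, whatever is discussed with a physician. Conversely, scenario can rise with no physician discussion. It therefore carries no direct information on this outcome.

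**Could other SAP text cover it?** Section 4 promises to look at the outcomes of interest by arm, but section 3 does not define physician discussion as one. Tertiary aim 1 concerns correlates of pursuit. The protocol lists its correlates separately from its secondary outcomes, and SAP 1.2.2 states that no formal hypotheses will be tested there. Neither provides an arm comparison.

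**Is a reason given?** No. By contrast, section 4.1.1 says openly that the Poisson/ZIP approach has been set aside.

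**The case against.** The strongest objection is the appendix. SAP 1.1.1 points to Table 2 for the primary and secondary aim, and 1.1.2 points to Table 3 for correlates of pursuit. Neither table is in the available text, and a physician-discussion row could be in either. This stands as a limit: the finding concerns the SAP body, and whether the plan as a whole omits the outcome cannot be determined. A table row alone would still leave the outcome without a definition or a model in sections 3 and 4.

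The protocol's commitment is also thin. It promises to measure these behaviours but gives no item wording, model or physician-specific hypothesis, and its reference to comparison in each arm is attached to the primary outcome and its components. That is fair. Even so, an arm comparison is the natural reading of a secondary outcome in a randomised trial.

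It might be argued that the later protocol date (December 21, 2022, against August 3, 2020 for the SAP) shows that the outcome was still active. That is weak evidence, because the protocol retains older text, such as the exclusion of prior transplants that its own note says was later relaxed. The mismatch does not depend on the dates.

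Finally, the consequence is limited: no bias in the main conclusion is shown. That is correct, and the weight given to the point reflects it.

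**Conclusion.** The concern holds. In the SAP body, one of three protocol secondary outcomes has no definition, no planned between-arm analysis and no stated reason for its absence, and the variable that replaces the list cannot detect it. The primary outcome is untouched and the other two behaviours are covered, so this should be corrected but does not threaten the trial's main result.

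The conclusion rests on the text alone, with no assumed rates. It is subject to the missing appendix tables. The questionnaire is also not supplied, so the existence, wording and response scale of the item are inferred from the protocol's plan to assess the behaviour.

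**What to change.** Add to SAP 3.1 a secondary outcome for patient-reported LDKT discussion with a physician, using the questionnaire item as collected. If it is yes/no, compare arms with one binomial GEE in the form of SAP 4.2.1 and 4.2.2:

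logit(p) = β₀ + β₁(Arm2) + β₂(Arm3) + β₃(4mo) + β₄(12mo) + β₅(Arm2×4mo) + β₆(Arm3×4mo) + β₇(Arm2×12mo) + β₈(Arm3×12mo)

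Report Arm 2 v Arm 1 and Arm 3 v Arm 1 in change from baseline: β₅ and β₆ at 4 months, β₇ and β₈ at 12 months. If only the follow-up times are responses, baseline may be a covariate instead; it should not serve in both roles. State how missing questionnaires and transplanted participants are handled, since the rules in SAP 4.2.3 are written for steps and do not transfer automatically. Date the addition, label it as made after some trial data were known, and report the result beside scenario whatever it shows.

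If the item was not collected or cannot be analysed, say so, justify its removal, and reconcile protocol section D, the SAP Study Overview and SAP 3.1.

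The cost is one further model on questionnaire data already planned, a few lines of SAP text including the missing-data rule, and one additional secondary test. The alternative costs a sentence of justification and aligned wording.
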